8.4.10. Assessment of Intensity

An event is defined as "serious" when it meets at least one of the predefined outcomes as described in the definition of an SAE (Section 8.4.2), NOT when it is rated as severe.

The severity (or intensity) of an AR or AE refers to the extent to which it affects the participant's daily activities. The Toxicity Grading Scale for Healthy Adult and Adolescent Volunteers Enrolled in Preventive Vaccine Clinical Trials (DHHS 2007) will be used to categorize local and

systemic reactogenicity events (solicited ARs), clinical laboratory test results, and vital sign measurements observed during this study. Specific criteria for local and systemic reactogenicity events are presented in Section 8.4.3.

The determination of severity for all unsolicited AEs should be made by the investigator based upon medical judgment and the definitions of severity as follows:

- Mild: These events do not interfere with the participant's daily activities.
- **Moderate**: These events cause some interference with the participant's daily activities and require limited or no medical intervention.
- **Severe**: These events prevent the participant's daily activity and require intensive therapeutic intervention.

Study staff should elicit from the participant the impact of AEs on the participant's activities of daily living to assess severity and document appropriately in the participant's source documentation. Changes in the severity of an AE should be documented in the participant's source documentation to allow an assessment of the duration of the event at each level of intensity to be performed. An AE characterized as intermittent requires documentation of onset and duration of each episode. An AE that fluctuates in severity during the course of the event is reported once in the eCRF at the highest severity observed.

8.4.11. Assessment of Causality

The investigator's assessment of an AE's relationship to IP is part of the documentation process but is not a factor in determining what is or is not reported in the study.

The investigator will assess causality (ie, whether there is a reasonable possibility that the IP caused the event) for all AEs and SAEs. The relationship will be characterized using the following classification:

- **Not related:** There is not a reasonable possibility of a relationship to the IP. Participant did not receive the IP OR temporal sequence of the AE onset relative to administration of the IP is not reasonable OR the AE is more likely explained by another cause than the IP.
- **Related:** There is a reasonable possibility of a relationship to the IP. There is evidence of exposure to the IP. The temporal sequence of the AE onset relative to the administration of the IP is reasonable. The AE is more likely explained by the IP than by another cause.

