8.4. Safety Definitions and Related Procedures

8.4.1. Adverse Event

An AE is defined as any untoward medical occurrence associated with the use of a drug/vaccine in humans, whether or not considered related to the drug/vaccine.

Events Meeting the Adverse Event Definition

- Exacerbation of a chronic or intermittent pre-existing condition including an increase in frequency and/or intensity of the condition, after the IP injection.
- New conditions detected or diagnosed after the IP injection even though they may have been present before the start of the study.

Events NOT Meeting the Adverse Event Definition

• Procedures planned before study entry (eg, hospitalization for preplanned surgical procedure).

- Medical or surgical procedure (eg, endoscopy, appendectomy): the condition that leads to the procedure should be the AE.
- Situations in which an untoward medical occurrence did not occur (social and/or convenience admission to a hospital).

An AR is any AE for which there is a reasonable possibility that the vaccine caused the AE (Section 8.4.3). For the purposes of IND safety reporting, "reasonable possibility" means that there is evidence to suggest a causal relationship between the vaccine and the AE.

An unsolicited AE is any AE reported by the participant that is not specified as a solicited AR in the protocol or is specified as a solicited AR but starts outside the protocol-defined period for reporting solicited ARs (ie, 7 days after vaccination).

An incidental, asymptomatic RT-PCR confirmed COVID-19 case (ie, workplace screening) should be reported as an unsolicited AE of "asymptomatic COVID-19" if occurring during the first 28 days post study vaccination unless the RT-PCR test was performed on the NP swab collected prior to study vaccination (Day 1).

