9.5.2. Safety Analyses

All safety analyses are descriptive in nature and will be based on the Safety Set, except summaries of solicited ARs, which will be based on the Solicited Safety Set. All safety analyses will be provided by study arm. Participants will be included in the vaccination group corresponding to what they actually received. Local solicited reactogenicity analysis will be presented by study group and for each injection content, respectively.

Safety and reactogenicity will be assessed by clinical review of all relevant parameters, including solicited ARs (local and systemic ARs); unsolicited AEs (including any clinical safety laboratory abnormalities); treatment-related AEs; severe AEs, SAEs, MAAEs, AESIs, and AEs leading to withdrawal from study participation; vital sign measurements; and physical examination findings.

The number and percentage of participants with any solicited local AR, with any solicited systemic AR, with any solicited AR during the 7-day follow-up period after each vaccination, and with any Grade 3 or higher solicited AR will be summarized. A 2-sided 95% exact confidence interval (CI) using the Clopper-Pearson method will be provided for the percentage of participants with any solicited AR.

The number and percentage of participants with unsolicited AEs, treatment-related AEs, severe AEs, SAEs, MAAEs, AESIs, and AEs leading to withdrawal will be summarized. Unsolicited AEs will be presented by MedDRA system organ class and preferred term. Unsolicited AEs will be coded according to the MedDRA Dictionary for AR Terminology.

The number of events of solicited ARs, unsolicited AEs/SAEs, MAAEs, AEs leading to withdrawal, and AESIs will be reported in summary tables accordingly. Pregnancy outcomes will also be summarized.

Table 9 summarizes the analysis strategy for safety parameters. For all other safety parameters, descriptive summary statistics will be provided. Further details will be described in the SAP.

 Table 9
 Analysis Strategy for Safety Parameters

Safety Endpoint	Number and Percentage of Participants, Number of Events
Any Solicited AR (overall and by local, systemic)	X
Any Unsolicited AE	X
Any SAE	X
Any Unsolicited MAAE	X
Any Unsolicited AESI	X
Any Unsolicited Treatment-Related AE	X
Any Treatment-Related SAE	X
Any Unsolicited AE Leading to Withdrawal From Study Participation	X
Any Severe Unsolicited AE	X
Any Treatment-Related Severe Unsolicited AE	X

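### Section 8.4.11 sets a reasonable-possibility test for causality, then adds comparative clauses that conflict with it and leave tied causes in neither category

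*Protocol*

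**What the plan says.** Section 8.4.11 of the protocol sets the question: "The investigator will assess causality (ie, whether there is a reasonable possibility that the IP caused the event) for all AEs and SAEs". The answer goes on a two-category scale.

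- *Related* opens with the statement that a reasonable possibility exists. It then lists exposure, reasonable timing, and "The AE is more likely explained by the IP than by another cause". Nothing marks these as alternatives.
- *Not related* opens with the statement that no reasonable possibility exists. It then lists three limbs joined by OR: no exposure, unreasonable timing, and finally "OR the AE is more likely explained by another cause than the IP".

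Section 8.4.1 uses the same term for an adverse reaction: "An AR is any AE for which there is a reasonable possibility that the vaccine caused the AE". It adds that, for IND safety reporting, the term "means that there is evidence to suggest a causal relationship between the vaccine and the AE". Neither sentence weighs one cause against another.

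Section 8.4.13 directs the causality judgement for every SAE to 8.4.11. Section 9.5.2 summarises treatment-related events, and Table 9 has three such rows: treatment-related unsolicited AEs, "Any Treatment-Related SAE", and treatment-related severe unsolicited AEs.

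**The concern.** A reasonable possibility and a more likely cause are different thresholds. The first asks whether the vaccine could credibly be responsible; the second asks whether it beats the competition. An event can pass the first and fail the second. Section 8.4.11 applies both at once and does not say which prevails when they disagree.

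What is at stake is the consistency and meaning of the relatedness field. Two investigators could each follow 8.4.11 and record the same event differently, one guided by the opening sentence and the other by the comparative limb. The protocol plans approximately 15 sites. Relatedness is recorded at site, so a statistical analysis plan can tabulate the field but cannot recover which test was applied.

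**Working it through.** No figure in the protocol depends on the causality wording. The nearest one, Table 7 in Section 9.3, follows from 1 − (1 − p)^n:

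- n = 50, p = 0.05: 92.3%
- n = 50, p = 0.03: 78.2%
- n = 100, p = 0.03: 95.2%
- n = 100, p = 0.02: 86.7%

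All four match the table. They concern observing any AE, related or not, so they do not size this point. The check is therefore one of wording.

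**Events run through both sections.** Assume that the participant was vaccinated, the timing is reasonable, and some evidence suggests a vaccine cause.

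| Event | 8.4.1 adverse reaction? | 8.4.11 *Related*? | 8.4.11 *Not related*? |
|---|---|---|---|
| Vaccine is the likelier cause | Yes | Yes, all elements met | No |
| Another cause is somewhat likelier | Yes | No, comparative clause fails | Last limb met, opening sentence contradicted |
| Vaccine and another cause equally likely | Yes | No, comparative clause fails | No limb met, opening sentence contradicted |

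**Second row.** The limbs of *Not related* are joined by OR, so a likelier alternative is sufficient on its own. Yet the category begins by denying the reasonable possibility that this event has. Section 8.4.11 is thus inconsistent internally, before 8.4.1 is considered. Against 8.4.1, the same event is an adverse reaction.

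**Third row.** *Related* needs the vaccine to be more likely, and the last limb of *Not related* needs the other cause to be more likely. A tie satisfies neither, and the other two limbs are excluded by exposure and timing. A two-category scale leaves this event no place.

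**What uses the classification.**

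- Table 9: the three treatment-related rows.
- Section 8.4.13: the SAE causality judgement.
- Section 8.4.3, note to Table 6: events of a solicited type that start more than 7 days after injection go to investigator causality assessment.

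**What does not use it.**

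- Primary endpoints (Section 3, Table 2): solicited reactions, unsolicited AEs, SAEs, AESIs, MAAEs and AEs leading to discontinuation are counted whatever the cause.
- Event recording (8.4.11 and 8.4.12): reporting does not depend on relatedness.
- Solicited reactions (8.4.3): all are treated as related to dosing.
- Pause rules (7.1, Tables 4 and 5): where cause matters, rules 1, 2, 6 and 7 carry their own attribution wording and do not cite 8.4.11.

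**Direction and size.** Measured against 8.4.1, the comparative clause can only take second-row events out of *Related*. For ties the direction is open, because a site could follow the opening sentence and record them as related. Sizing the effect would need the share of unsolicited AEs with a competing cause at least as likely as the vaccine, and how sites resolve the conflict. The protocol gives neither.

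**The case against.** The strongest defence has three parts.

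First, the explanation of reasonable possibility in 8.4.1 is stated for IND safety reporting, and investigators are sent to 8.4.11 to classify events. That is correct and narrows the conflict between the sections. It does not remove it. The adverse-reaction definition in 8.4.1 carries no such limit, and 8.4.13, which covers SAE reporting under 21 CFR Part 312, itself points to 8.4.11. The conflict inside 8.4.11 stands in any case.

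Second, under-classification is not compelled. An investigator who sees a reasonable possibility contradicts the first sentence of *Not related* by choosing it. This also stands: the text is ambiguous, and recording such events as not related is one permitted reading. Ambiguity in a site-level classification is nonetheless the defect.

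Third, what remains is descriptive. No primary endpoint, pause rule or recording duty turns on relatedness, and every SAE goes to the sponsor within 24 hours. This stands in full and sets the weight of the point.

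A reader might go further and infer any of the following; the documents support none of them.

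- *The bar becomes a probability above 50%.* The comparison is with another cause. With assumed probabilities of 40% for the vaccine and 30% for each of two alternatives, the vaccine is likelier than either and still below 50%.
- *Dose selection is biased.* The same wording applies to every arm, endpoint assessors are blinded (9.1), and all-cause data are available for comparing arms. Nothing indicates that misclassification would differ by dose.
- *The primary safety results are understated.* They do not use the classification.

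**Conclusion.** The point holds as a conflict of wording with limited reach. Section 8.4.11 contradicts its own opening sentences and the adverse-reaction definition in 8.4.1 when another cause is somewhat likelier, and it provides no category when causes are tied. The effect is confined to the three treatment-related rows of Table 9 and the causality judgement for SAEs. No size can be given from the documents.

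The conclusion rests on reading the elements of *Related* as cumulative, since no OR separates them, and the limbs of *Not related* as alternatives, since OR joins them. It is worth correcting because the ambiguity enters when sites record the data and analysis cannot undo it.

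**What to change.** Reconcile 8.4.11 with 8.4.1 so that reasonable possibility is the only test:

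1. Delete "The AE is more likely explained by the IP than by another cause" from *Related*.
2. Reword the limb "OR the AE is more likely explained by another cause than the IP" so that another cause supports *Not related* only when no reasonable possibility of a relationship to the vaccine remains. Examples in the eCRF guidance can preserve practical direction for sites.

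Every event then falls into exactly one category.

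The cost is two clauses, matching eCRF guidance and a note to sites. Somewhat more events will be labelled related. First enrolment was estimated for May 2022 and Amendment 2 is dated 16 August 2022, so some events may already have been classified under the present wording. Those should be flagged or re-assessed, with assessors still blinded, so that the treatment-related summaries do not mix two standards unmarked.

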8.4.12. Reporting Adverse Events

The investigator is responsible for reporting all AEs that are observed or reported during the study, regardless of their relationship to IP or their clinical significance. If there is any doubt as to whether a clinical observation is an AE, the event should be reported.

All unsolicited AEs reported or observed during the study will be recorded on the AE page of the eCRF. Information to be collected includes type of event, time of onset, investigator-specified assessment of severity (impact on activities of daily living) and relationship to IP, time of resolution of the event, seriousness, as well as any required treatment or evaluations, and outcome. The unsolicited AEs resulting from concurrent illnesses, reactions to concurrent illnesses, reactions to concurrent medications, or progression of disease states must also be reported. All AEs will be followed until they are resolved or stable or judged by the investigator to be not clinically significant. The Medical Dictionary for Regulatory Activities (MedDRA) will be used to code all unsolicited AEs.

Any medical condition that is present at the time of screening but does not deteriorate should not be reported as an unsolicited AE. However, if it deteriorates at any time during the study, it should be recorded as an unsolicited AE.

8.4.13. Reporting Serious Adverse Events

Prompt notification by the investigator to the Sponsor of an SAE is essential so that legal obligations and ethical responsibilities toward the safety of participants and the safety of a study intervention under clinical investigation are met.

Any AE that meets SAE criteria (Section 8.4.2) must be reported to the Sponsor immediately (within 24 hours of becoming aware of the SAE) via the EDC system. The investigator will assess whether there is a reasonable possibility that the IP caused the SAE as described in Section 8.4.11.

If the eCRF is unavailable at the time of the SAE, the paper SAE/AESI reporting form provided by the Sponsor is to be used for SAE reporting.

The Sponsor will be responsible for notifying the relevant regulatory authorities of any SAE as outlined in 21 US CFR Parts 312 and 320. The investigator is responsible for notifying the institutional review board (IRB) directly. Regulatory reporting requirements for SAEs are described in Section 8.4.18.

The investigator and any qualified designees are responsible for detecting, documenting, and recording events that meet the definition of an AE, including SAEs, and remain responsible for following up AEs that are serious, considered related to IP or study procedures, or caused the participant to discontinue the study until they are considered resolved or clinically stable, per the investigator's judgement.

8.4.14. Reporting of Adverse Events of Special Interest

The following process for reporting an AESI ensures compliance with 21 CFR 312 and ICH GCP guidelines. After learning that a participant has experienced an AESI, the investigator or

designee is responsible for reporting the AESI to the Sponsor, regardless of relationship or expectedness, within 24 hours of becoming aware of the event. If the AESI meets the criteria for an SAE, the SAE reporting procedure should be followed.

8.4.15. Time Period and Frequency for Collecting Adverse Event and Serious Adverse Event Information

Medical occurrences that begin before IP dosing but after obtaining informed consent will be recorded in the Medical History/Current Medical Conditions section of the eCRF and not in the AE section; however, if the condition worsens at any time after IP administration, it will be recorded and reported as an AE.

Adverse events may be collected as follows:

- Observing the participant.
- Receiving an unsolicited complaint from the participant.
- Questioning the participant in an unbiased and nonleading manner.

Solicited ARs will be collected from the day of injection through 6 days after vaccination. Other (unsolicited) AEs will be collected from the day of injection through 28 days after vaccination.

Serious AEs (including AESIs) will be collected from the start of IP dosing until the last day of study participation.

All SAEs and AESIs will be recorded and reported to the Sponsor or designee immediately, and under no circumstance should this exceed 24 hours of becoming aware of the event via the EDC system. If a site receives a report of a new SAE or AESI from a study participant or receives updated data on a previously reported SAE or AESI and the eCRF has been taken offline, then the site can report this information on the paper SAE/AESI report form provided by the Sponsor.

An abnormal value or result from a clinical or laboratory evaluation can also indicate an AE if it is determined by the investigator to be clinically significant (eg, leads to study drug discontinuation or meets any serious criteria). If this is the case, it must be recorded in the source document and as an AE on the appropriate AE form(s). The evaluation that produced the value or result should be repeated until that value or result returns to normal or is stabilized and the participant's safety is not at risk.

Investigators are not obligated to actively seek AEs or SAEs after EoS participation. However, if the investigator learns of any SAE (including a death) at any time after a participant has withdrawn from or completed the study and the investigator considers the event to be reasonably related to the IP or study participation, the investigator must promptly notify the Sponsor.

Participants who develop ILI will be followed through 30 days from the onset of ILI, even if Day 30 is beyond Day 181/EoS.

8.4.16. Method of Detecting AEs and SAEs

Electronic diaries have specifically been designed for this study by the Sponsor. The diaries will include prelisted AEs (solicited ARs) and intensity scales; they will also include blank space for the recording of information on other AEs (unsolicited AEs) and concomitant medications/vaccinations.

The investigator is responsible for the documentation of AEs regardless of study arm or suspected causal relationship to IP. For all AEs, the investigator must pursue and obtain information adequate to determine the outcome of the AE and to assess whether the AE meets the criteria for classification as an SAE requiring immediate notification to the Sponsor or its designated representative.

Care will be taken not to introduce bias when detecting AEs and/or SAEs. Open-ended and nonleading verbal questioning of the participant is the preferred method to inquire about AE occurrences.

8.4.17. Follow-up of AEs and SAEs

After the initial AE/SAE report, the investigator is required to proactively follow each participant at subsequent visits and contacts.

All AEs and SAEs will be treated as medically appropriate and followed until resolution, stabilization, the event is otherwise explained, or the participant is LTFU, as defined in Section 7.4.

8.4.18. Regulatory Reporting Requirements for SAEs

Prompt notification by the investigator to the Sponsor of an SAE is essential so that legal obligations and ethical responsibilities toward the safety of participants and the safety of a study intervention under clinical investigation are met.

The Sponsor has a legal responsibility to notify both the local regulatory authority and other regulatory agencies about the safety of a study intervention under clinical investigation. The Sponsor will comply with country-specific regulatory requirements relating to safety reporting to the regulatory authority, IRBs, and investigators.

Investigator safety reports must be prepared for suspected unexpected serious ARs according to local regulatory requirements and Sponsor policy and forwarded to investigators as necessary.

An investigator who receives an investigator safety report describing an SAE or other specific safety information (eg, summary or listing of SAEs) from the Sponsor will review and then file it along with the IB and will notify the IRB, if appropriate according to local requirements.

8.5. Safety Monitoring Committees

8.5.1. Internal Safety Team

An internal safety team, inclusive of, at a minimum, the Sponsor's medical monitor, Sponsor's safety physician, and a CRO medical monitor, will be formed to review interim and cumulative blinded safety data on a regular basis with a remit to escalate concerns to the DSMB. The IST will conduct a scheduled review of safety data after at least 55 participants (approximately 5 participants in Group 1 and approximately 10 participants in Groups 2 to 6) (see Table 3) have completed the Day 8 visit. Enrollment will be ongoing while this review is conducted if no pause rules (Section 7.1) have been met and the study team has not identified any safety concerns. The IST will also conduct ad hoc reviews as requested by the study medical monitor and the study team.

